### 1.2 Study Design and Randomization

The study is a parallel-group Randomized Control Trial with up to 384 participants recruited from family planning sites in Duval County, Florida and randomized 1:1 into two groups (192 in intervention group, 192 in control). Study duration: 3 months.

Treatment: Participants in this arm will receive the HIV prevention DST intervention and will receive the intervention immediately before their provider visit.

Control: Participants in this arm will receive usual care.

Randomization procedures: Randomization will be implemented using randomly permuted blocks of randomly selected size 2 and 4, stratified by clinic and race. All randomization will occur by research staff with the use of a REDCap randomization instrument.

### 1.3 Study Population

Inclusion Criteria:

- Identify as a woman
- Age 18 years old to 45
- Not known to be living with HIV
- Not known to be taking PrEP
- English speaking
- Interested in participating in the study

Exclusion Criteria:

- Unable to consent
- Currently using PrEP
- Cisgender men
- Unwilling to be contacted in 3 months
- Already participated in the study

### 1.4 Intervention

HIV Prevention Decision Support Tool (DST): The tool is founded on principles of decision-science and developed in a systematic manner including pilot testing. The tool will present HIV prevention information through a tablet in the clinical setting. The decision support tool will address barriers to PrEP delivery, including 1) limited client knowledge about PrEP, 2) limited time to educate patients in busy clinics, 3) women's lack of knowledge of their own HIV vulnerability, and 4) hesitancy of women to initiate discussions about PrEP with providers due to judgmental attitudes and stigma. Also, the tool emphasizes the highly variable and individual nature of baseline risk.

### 1.5 Sample size calculation

Using standard methods, we estimate that a sample of 320 women will provide 80% power in two-sided tests with alpha of 0.05 to detect a between-group difference of 10 percentage points in PrEP uptake, from 5% among controls to 15% in the intervention arm. This estimate is conservative, for two reasons. First, in addition to multiple imputation, which will capture some information from women with missing 3-month outcomes, we will enroll 384 women to protect against a loss to follow-up of up to 20%. Second, because women rather than providers will be randomized, any within-provider clustering of outcomes will increase precision in the proposed mixed models including random effects for provider.

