## 2. Population of analysis

We will conduct an intention to treat (ITT) analysis as well as a per protocol (PP) analysis. ITT will serve as our primary analysis. For PP analyses, individuals in the intervention group will be considered members of the control group if they did not receive or did not interact with the DST for even one minute.

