- Willingness to Use the Decision Support Tool at Future Visits: Participants in the experimental arm will be asked about whether they would use the tool again if they returned to the clinic. Response options are "yes", "no", "unsure".
- Recommend the Decision Support Tool: Participants in the experimental arm will be asked whether they would recommend the tool a friend. Response options are "yes", "no", "unsure".
- Satisfaction with the Decision Support Tool: Participants in the experimental arm will be asked about the degree to which they were satisfied with the information in the tool. Response options vary from 1-5: "very unsatisfied" to "very satisfied".
- HIV Prevention Method Use (any method – planned or new method): A self-reported measure of HIV prevention method use, including those who reported discontinuing the initial HIV prevention method(s) that were reported post-clinic visit. A response of "yes" to any of the following questions: since your [baseline] visit, have you used....for HIV prevention – abstinence, condoms, PEP, PrEP, regular HIV testing, treatment as prevention, regular sexually transmitted disease (STD) testing, other method. The outcome will be dichotomized to those who responded affirmatively vs other responses ("no"/"unsure").
- **HIV Prevention Method Continuation:** A self-reported measure of HIV prevention method continuation.

- **HIV Prevention Method Use:** A self-reported measure of HIV prevention method use, including those who reported discontinuing the initial HIV prevention method(s) that were reported post-clinic visit.

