#### 3.3.1 Primary analysis (H1)

PrEP prescriptions within 3 months of primary study visit will be extracted from participants' electronic medical records (EMRs). Data will be matched to survey data using participant medical record numbers (MRNs). Summary statistics will be presented by treatment group. Differences in PrEP prescriptions between groups will be examined by  $\chi^2$  or Fisher's exact-tests as appropriate. Effect size will be calculated.

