#### 3.3.2 Secondary data analyses

The analysis plan for H2-H9 is as follows:

Summary statistics will be presented by treatment group. Differences between study groups at  $t_1$  will be assessed through  $\chi^2$  or Fisher's exact tests as appropriate. Cohen's d will be calculated as measure for effect size.

The analysis plan for H10 is as follows:

Full scale and subscales will be scored as instructed in the [Decisional Conflict Scale](#) manual. Summary statistics will be presented by treatment group for the full scale and by subscale. To assess differences in scale score distribution between groups, we will perform t-tests or sign tests as appropriate. In case of high positive skew (as common in the literature) we will create binary variables demarcating no conflict versus any conflict and perform  $\chi^2$  tests. Cohen's d will be calculated as measure for effect size.

The analysis plan for H11-H13 is as follows:

Summary statistics will be presented by treatment group. Differences between study groups at  $t_2$  will be assessed through  $\chi^2$  or Fisher's exact tests as appropriate. Cohen's d will be calculated as measure for effect size.

The analysis plan for H14-H18 is as follows:

Summary statistics will be presented for the intervention group.

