### 4.2 Missing data

We will report proportions of missing values for all collected variables where needed. Baseline characteristics missing data will be imputed by multiple imputation with chained equations (MICE) procedures as appropriate.

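### 384 women keep the required 320 only up to 16.7% loss, not 20%, and two methods cited in calling the estimate conservative are missing from the analysis sections

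*SAP*

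**What the plan says.** SAP 1.5, repeated in Protocol 7.2, sets 320 women as the number giving 80% power at two-sided 0.05 for PrEP uptake of 5% in controls and 15% with the tool. It calls this conservative for two reasons.

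- The first combines imputation, "in addition to multiple imputation, which will capture some information from women with missing 3-month outcomes", with over-enrolment: "we will enroll 384 women to protect against a loss to follow-up of up to 20" percent.
- The second is that "any within-provider clustering of outcomes will increase precision in the proposed mixed models including random effects for provider".

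The analysis sections read differently.

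- SAP 3.3.1 (H1): "Differences in PrEP prescriptions between groups will be examined by" chi-square or Fisher's exact tests. The outcome is a PrEP prescription taken from the medical record.
- SAP 3.3.2: chi-square or Fisher for H2–H9 at the post-visit survey; t, sign or chi-square tests for H10; chi-square or Fisher for H11–H13 at three months; summaries only for H14–H18.
- SAP 4.2: "Baseline characteristics missing data will be imputed by multiple imputation with chained equations (MICE) procedures as appropriate".
- SAP 2: "ITT will serve as our primary analysis", with nothing on women who do not answer the 3-month survey.
- Protocol 10.1 refers quantitative analysis to the SAP, so it supplies nothing further.

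**The concern.** There are two separate faults in one paragraph. First, the attrition allowance does not match the numbers beside it: taking 20% from 384 does not leave 320. Second, two of the features offered as making the estimate conservative depend on methods that the analysis sections never specify. An unadjusted two-group test uses only arm and outcome, so it cannot gain precision from provider clustering. An imputation rule confined to baseline characteristics recovers nothing about missing outcomes.

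At stake are the accuracy of a stated design property and, more practically, how the 3-month self-reports will be analysed. Someone relying on SAP 1.5 would impute missing responses. Someone relying on SAP 3.3.2 and 4.2 would analyse responders only. That choice should be settled before results are seen.

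**Working it through.** **Inputs.** Rates 5% and 15%, two-sided alpha 0.05, power 80%, 320 required, 384 enrolled, loss up to 20% (SAP 1.5, Protocol 7.2); 1:1 allocation, 192 per arm (SAP 1.2). The plan says only that standard methods were used, so the formula behind 320 is inferred.

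**Reproducing 320.**
- Uncorrected, pooled variance under the null: n = [1.96·√(2·0.10·0.90) + 0.8416·√(0.05·0.95 + 0.15·0.85)]² / 0.10² = 140.1 per arm, so 141 per arm and 282 in total.
- Continuity-corrected: n′ = (140.1/4)·[1 + √(1 + 4/(140.1·0.10))]² = 159.5 per arm, so 160 per arm and **320 in total**. This matches the plan.

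**Attrition.**
- 320 × 1.20 = 384, which is how the enrolled number arises.
- 384 × 0.80 = 307.2, about 13 short of 320.
- 384 − 320 = 64, and 64/384 = **16.7%**, the largest loss that keeps 320.
- 20% of 384 is 76.8, about 77 women.
- For reference, 320/0.80 = 400.

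**Power for 5% versus 15%.** The continuity-corrected formula is Φ{[0.10 − 1/n − 1.96·√(0.18/n)] / √(0.175/n)} with n per arm. The uncorrected formula omits 1/n. Exact values come from full enumeration of both binomials. Ranges at 307 cover the two splits, 153/154 and 154/153.

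| Basis | 320 | 307 | 384 |
|---|---|---|---|
| Continuity-corrected formula | 80.1% | 78.3% | 87.5% |
| Uncorrected formula | 85.0% | 83.5% | 90.7% |
| Exact, Pearson chi-square | 86.8% | 85.2–85.3% | 92.1% |
| Exact, Yates chi-square | 81.6% | 80.1–80.4% | 89.1% |
| Exact, Fisher | 82.4% | 81.4–84.8% | 89.1% |

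The 384 column assumes that charts are extracted for every randomized woman. Protocol 3.2.6 does not say whether that includes women who dis-enroll.

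**Methods cited against methods specified.**

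| Cited in SAP 1.5 | Where it should appear | What is there |
|---|---|---|
| Imputation of missing 3-month outcomes | SAP 4.2 | Baseline characteristics only |
| Mixed models with provider random effects | SAP 3.3.1–3.3.2 | No model and no provider term |
| Enrolment beyond 320 | SAP 1.2 | 384 planned; present |

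**Which outcomes depend on the 3-month survey.**
- H1 does not. Protocol 3.2.5 has medical record numbers collected at the visit and submitted for extraction, with no condition on survey response.
- H11–H13 do ("The analysis plan for H11-H13 is as follows", tested at three months).
- H2, reported PrEP initiation, appears to. SAP 2.1.2.2 collects reported PrEP use at follow-up and SAP 1.6 asks about initiation at three months, yet SAP 3.3.2 tests H2 at the post-visit survey.

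**Event counts.** If self-reported use matched the assumed 5%, about 153.5 × 0.05 = 7.7 control events would be expected at 307 women. This does not carry over to H12, which counts any of "abstinence, condoms, PEP, PrEP, regular HIV testing, treatment as prevention, regular sexually transmitted disease (STD) testing, other method". The documents give no expected rates for H12 or H13.

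**The case against.** The strongest reply is that nothing is lost in practice. Both tests named for H1 keep at least 80% exact power at 307 women. On the uncorrected formula only 282 are needed, so 384 would tolerate about 26% loss (1 − 282/384 = 26.6%). The allowance also concerns follow-up, whereas the powered outcome is read from charts. And over-enrolment, half of the first reason, is a genuine safeguard.

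All of this stands, and it limits the size of the point. It does not make 20% the right figure for the stated 320, and it does not put the missing methods into SAP 3.3 or 4.2.

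Two stronger readings are tempting and should be resisted.

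- A reader might infer that the trial is underpowered, or must enrol 400. The documents do not support this. The sub-80% figure arises only on the inferred continuity-corrected formula, and survey non-response does not by itself remove a woman from H1.
- A reader might infer that the primary analysis is undefined because a mixed model is mentioned in one place and a chi-square test in another. SAP 3.3.1 names the test and SAP 2 names the population, so the H1 analysis is not in doubt.

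**Conclusion.** The point holds with modest consequences. The attrition figure is wrong as arithmetic: 16.7% (64 women), not 20%, is the loss at which 384 still leaves 320. This needs no assumption beyond the plan's own numbers. Of the supports for calling the estimate conservative, over-enrolment is valid; outcome imputation and provider mixed models have no counterpart in the specified analyses.

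For H1 the cost of 20% loss is about 2 percentage points on either the continuity-corrected or the exact Pearson basis. Power stays at or above 80% under exact Pearson and Fisher, given the assumed 5% and 15%. The more substantive gap is the unsettled handling of missing 3-month self-reports (H11–H13, and H2 if it rests on follow-up data) when ITT is declared primary. How far dis-enrolment reduces the chart-based sample cannot be judged from the documents.

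**What to change.** (a) In SAP 1.5 and Protocol 7.2, replace the 20% allowance with up to 16.7% (64 of 384). Add that the primary outcome is taken from charts, so loss to the 3-month survey does not by itself remove a woman from it. If power at other sample sizes is quoted, name one basis and use it throughout. No extra enrolment is needed.

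(b) In both documents, delete the provider mixed-model sentence from the rationale. Alternatively, add the model to SAP 3.3.1 as a named sensitivity analysis, with chi-square/Fisher kept as primary.

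(c) Make SAP 1.5 and 4.2 agree for all 3-month self-reports: H11–H13 and also H2, after reconciling its follow-up data source with the post-visit test time in SAP 3.3.2. Either extend MICE in SAP 4.2 to these outcomes, with complete-case analysis as sensitivity, or delete the imputation clause from both documents and state that these outcomes are analysed as randomized among responders, so that the departure from full ITT is explicit.

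The cost of (a) and (b) is wording, a less favourable attrition figure and one reason fewer for calling the estimate conservative. Keeping MICE or the mixed model adds modest analysis work and may be unstable with few PrEP events. Choosing responders only gives up the information that imputation was meant to recover.

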### 1.6 Study Procedures

Both groups will complete surveys at three measurement timelines: baseline ( $t_0$ ), immediately post-appointment ( $t_1$ ), and at 3-months ( $t_2$ ). Data collection will occur via electronic survey hosted on RedCAP. Neither the participants nor the study team will be blinded.

Research assistants will approach eligible patients in the clinic waiting room prior to their appointments. They will assess eligible and complete consent procedures in private location on site. Participants will then complete a baseline questionnaire on a tablet. After completion of initial questionnaire, participant will be randomized to a treatment using a randomization module in RedCAP. Participants randomized to the intervention group will then immediately receive access to the DST via a tablet provided by the research assistant to review in advance of their clinical visit.

After the participant's visit with the provider, they will be asked to complete a post-visit survey about their clinic visit and counseling, risk perception, decision making, sexual history, and their experience with the decision support tool if they are in the intervention arm.

Three months post-visit, research staff will follow-up with participants by phone, email, or SMS to administer a short survey and ask participants about their chosen HIV prevention method, and if they initiated PrEP.

Upon completion of the study, research staff will extract data from the medical record pertaining to participants' PrEP prescriptions, history of sexually transmitted infections, zip code, and insurance status.

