3.2.2 Blinding

Given the nature of the intervention, blinding of participants to which intervention they receive (DST or not) will not be feasible. Clinicians and counselors in the clinic will not be alerted to whether participants used the DST or not; however, participants may discuss information in the DST, unmasking the study arm. Consequently, clinicians and counselors will unlikely be blinded to study interventions. However, at follow-up, study personnel conducting surveys by phone will not be aware of participants’ study arm; assignment will be concealed in a different page of the participant’s record. Consent forms intentionally do not disclose the specific outcome of interest (i.e. PrEP initiation), so as not to influence participant behavior. Additionally, participants will not be aware of their arm assignment until after they have been consented. Study staff will be blinded during quantitative data analysis of participants use of the DST or not. Qualitative data will not be blinded as study participants will be asked about use of the DST.

3.2.3 Baseline procedures (see below changes we will be making to the study procedures based on COVID-19)

Patients

The baseline procedures for patient participants are as follows:

On the day of enrollment:

- Individuals will be handed a laminated information card about the study and eligibility criteria when they present to the front desk for check in. Eligibility criteria on this sheet will include:
 - Identify as a woman
 - Age 18 years old or over
 - Not known to be living with HIV
 - Not known to be taking PrEP
 - English speaking
 - Interested in participating in the study
- If patients self-identify as eligible and interested in learning more about the study, they will be instructed to hold onto the laminated card (indicating to the research assistant that they would like to be approached). If they are not interested in participating, patients will hand this card back to front desk staff.
- Research staff will approach patients who have held onto the card in the clinic waiting room before their appointment and invite them to be screened for study eligibility in a semi-private space. Research staff will share a brief description of the study and assess eligibility using a verbal eligibility checklist.

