3.2.4 Patient participant follow-up surveys

Each study participant will be contacted by whatever method they prefer (phone, mail, SMS, email, in person at a follow-up medical visit) three months after their study visit to complete a follow-up survey.

The survey will be completed either over the phone with an RA or in the patient's own time, online, using REDCap.

- Patient contact information and enrollment dates will be entered into REDCap at baseline, where follow-up contact due dates will be calculated. RAs will conduct

follow-up attempts via the patient's preferred method, logging each attempt and its outcome in REDCap.

- Participants' study arm assignment will be concealed in a different page of the participant's record, and study personnel will not look up assignment.
- Google Voice will be used for text and phone follow-up contact attempts. By using Google Voice as the platform from which to make calls and send text messages, no personal cell phones will have saved participant information on them. Record of contact with participants will be deleted from the Google Voice account monthly by RAs (i.e. call logs). In the case that we are unable to use Google Voice, we will use study staff landlines to call study participants where no participant information will be saved.
- Contact attempts for the 3 month survey will be declared unsuccessful after 4 weeks.
- \$10 gift certificates for completed surveys will be mailed, or picked up at the FDOH office or clinic if the patient prefers, through coordination with the RAs. For more detail on participant payments, see Section 6.

3.2.5 **Medical record data**

In addition to the above procedures, after participants consent to the study, research staff will obtain participants' medical record numbers (MRN) on the day of their visit. At the conclusion of each day, research assistants will request medical record numbers based on patient names and date of birth on the schedule from clinic staff. Participants who consented to the study will have their medical record number entered into a secure REDCap form that is separate from study survey responses, and links study identification numbers to medical record numbers. Access to this REDcap form will be restricted to FDOH employees, and is password protected on secure servers. RAs will shred the paper copy in the clinic after the MRN entered electronically.

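### SAP 1.6 contradicts protocol 3.2.2 and 3.2.4 on whether the 3-month phone surveyors and the quantitative analysts are blinded

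*SAP*

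**What the plan says.** **SAP 1.6 (Study Procedures):** "Neither the participants nor the study team will be blinded". No exception is made for follow-up callers or analysts.

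**Protocol 3.2.2 (Blinding)** separates the roles:
- Participants: "blinding of participants to which intervention they receive (DST or not) will not be feasible". This agrees with the SAP.
- Clinicians and counselors are not told the arm, but the protocol expects them to be unmasked in practice.
- Follow-up: "study personnel conducting surveys by phone will not be aware of participants’ study arm".
- Analysis: "Study staff will be blinded during quantitative data analysis of participants use of the DST or not".
- Participants' expectations: "Consent forms intentionally do not disclose the specific outcome of interest (i.e. PrEP initiation), so as not to influence participant behavior".

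**Protocol 3.2.4** says how the follow-up blinding works: "Participants' study arm assignment will be concealed in a different page of the participant's record, and study personnel will not look up assignment". The same section lets participants answer either by phone with a research assistant or online on their own.

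**Protocol 10.1** contains no quantitative methods and refers the reader to the SAP.

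**The concern.** The SAP is the document the analyst will work from, and it says that no one on the team is blinded. Two things depend on which text is followed.

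**Interviewing.** Self-reported PrEP use, use of any prevention method and continuation at 3 months (SAP hypotheses H2 and H11 to H13) may be taken by a research assistant over the phone. An interviewer who knows the arm may prompt or record answers differently. Under protocol 3.1, research assistants also carry out intervention activities. Neither document says that the person who randomized a woman or gave her the tablet will not be the one who calls her.

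**Analysis choices.** SAP 3.1 and 3.3.2 leave several decisions until the data have been seen: merging sparse categories, turning skewed scales into binary variables, and choosing a t-test or a sign test. No cell-size or skewness threshold is given. For decisional conflict the SAP names the split (none versus any), but not how much skew triggers it. An analyst who knows the arm could, even unintentionally, choose the version that favors the DST.

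**Working it through.** **1. Texts side by side**

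| Role | SAP 1.6 | Protocol 3.2.2 / 3.2.4 | Agree? |
|---|---|---|---|
| Participants | not blinded | not feasible | yes |
| 3-month phone surveyors | not blinded (study team) | blinded, arm on a separate page of the record | no |
| Quantitative analysts | not blinded (study team) | blinded | no |

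**2. Which outcomes are exposed**

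- *Primary outcome.* A PrEP prescription in the chart, extracted by the health department's IT unit into a file of study IDs and outcome variables (protocol 3.2.5), and tested by chi-square or Fisher's test (SAP 3.3.1). No interviewer is involved, and little is left to the analyst.
- *Post-visit outcomes* (perceived risk, decisional conflict, satisfaction, intention and similar). Normally entered on a tablet by participants who know their arm (protocol 7.3). Blinding the follow-up caller never protected these. Blinding the analyst does bear on how they are collapsed, dichotomised and tested.
- *3-month self-reports.* Interviewer blinding matters here, for phone completions only. SAP 3.3.2 groups H2 with the post-visit comparisons, but SAP 2.1.2.2 collects self-reported PrEP use at follow-up.

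**3. Size**

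The plan gives no figure on blinding. Its sample size reproduces and does not depend on which text is followed. For 5% versus 15%, the two-proportion formula gives

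n = [1.96√(2×0.10×0.90) + 0.842√(0.05×0.95 + 0.15×0.85)]² / 0.10² = 140.1 per arm,

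and the continuity correction gives (140.1/4)×[1 + √(1 + 4/(140.1×0.10))]² = 159.5. That is 160 per arm, or 320 in total.

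Inputs for the illustration:
- Respondents: 384 × (1 − 0.20) = 307.2, or about 154 per arm (SAP 1.2 and 1.5).
- True rate of PrEP use: 5% in both arms. This is the SAP's control rate for prescriptions, borrowed here as an assumption.
- Excess false yes answers in the DST arm: 1 to 5 percentage points. This is assumed, because the documents give no value.
- Two-sided test at 0.05.

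Normal approximation for a 3-point excess (5% versus 8%):
- Pooled rate 0.065, so SE₀ = √(2×0.065×0.935/154) = 0.0281.
- SE₁ = √[(0.05×0.95 + 0.08×0.92)/154] = 0.0280.
- Φ[(0.03 − 1.96×0.0281)/0.0280] = Φ(−0.89) ≈ 0.186. The opposite tail adds less than 0.001, so the rejection rate is about 18.7%.

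Exact enumeration, summing the binomial probabilities of every pair of counts that the test rejects:

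| Excess (points) | Chi-square, uncorrected | Fisher's |
|---|---|---|
| 0 | 4.9% | 2.5% |
| 1 | 6.4% | 3.7% |
| 2 | about 11% | 7.1% |
| 3 | 17.9% | 12.9% |
| 5 | about 38% | about 31% |

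The effect is smaller at a higher base rate. With a true rate of 15% and 160 per arm, the normal approximation gives 5.7%, 7.8%, 11.1% and 21.7% for the same four excesses.

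The excess is averaged over the whole DST arm. Three points is 0.03 × 154 = 4.6 false yes answers. If half the women answered online, an overall excess of 3 points would need 6 points among those answering by phone. The table says nothing about the effect of analyst discretion, which cannot be quantified from the documents.

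**The case against.** The strongest reply is that the SAP sentence is one loose line in an overview of procedures. It orders no one to reveal the arm. The operating rule is in protocol 3.2.4, and the SAP does not cancel it. This is right as far as it goes: the documents show conflicting wording, not that follow-up or analysis was actually run unblinded. But the sentence has no exceptions, and the protocol sends the analyst to the SAP, so the conflict cannot be left to interpretation.

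A reader might infer that following the SAP removes the trial's only protection for its self-reported outcomes. The documents do not support that. The consent forms withhold the outcome of interest, the 3-month survey can be completed online without an interviewer, and the data for the primary analyses are cleaned and locked first (protocol 8.3). Nor does interviewer blinding cover self-reports in general. It covers those taken by phone at 3 months.

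It would also be too strong to say that data-dependent choices are safe only under analyst blinding. Numerical triggers written into SAP 3.1 and 3.3.2 would limit the same discretion by another route. The SAP has none, so analyst blinding is the main safeguard stated.

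Finally, a coded arm label alone would not blind the analyst. The DST-experience items exist only in the intervention arm, and the per-protocol rule in SAP section 2 uses data on DST use. This stands, and the fix allows for it.

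**Conclusion.** The contradiction is real and lies in current text. It should be corrected. It does not undermine the primary analysis, because that outcome comes from the chart and its test leaves little discretion.

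What is at stake is narrower: interviewer blinding for the 3-month phone reports, and analyst blinding for the threshold-free choices in the secondary outcomes. Any size is conditional on assumption. At a 5% true rate and about 154 per arm, a 1 to 5 point reporting excess puts the chi-square false-positive rate at roughly 6% to 38%, and Fisher's at about 4% to 31%. These rates apply only to the part of the bias that comes from an interviewer who knows the arm.

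**What to change.** Replace the sentence in SAP 1.6 with the protocol's rule: participants and the on-site staff who recruit and randomize are not blinded; the staff conducting 3-month phone surveys and the quantitative analysts are. State what each group is blinded to and until when, and whether a follow-up caller may be someone who handled that participant's allocation.

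Hold the arm as a coded A/B variable. Keep the DST-only items and the DST-use data in a separate file. Release both only when the data are locked and every collapsing, transformation and test choice has been recorded.

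The cost is one sentence in the SAP, a coded variable and a split file. The small downside is that the DST-only summaries (H14 to H18) and the per-protocol analysis must wait until after unmasking. The sample size and the primary test do not change.
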